2.2 Study Design

2.2.1 Overview of Study Design

This is a single-arm, open-label phase II study of cabozantinib in subjects with malignant pheochromocytomas and paragangliomas. The primary endpoint is to estimate best overall response rate by RECIST 1.113 in patients with measurable disease determined by a. CT or b. MRI.

The primary objective is to estimate the best overall response rate in patients with measurable disease. Response will include RECIST 1.1 CR, PR, and SD. With 14 patients, the 95% confidence interval for a 45% response rate would be (18.9, 71.1%). For the exploratory objective in the small group of patients with bone metastases, the 95% confidence interval for a 45% response rate with 8 patients would be (10.5, 79.5%). We do not include a formal statistical monitoring rule for toxicity given the established safety profile of this drug.

Continuous variables will be summarized using descriptive statistics such as mean, standard deviation, median and range. Categorical variables will be tabulated by frequencies and the corresponding percentages. Response rates and their 95% confidence intervals will be estimated. Kaplan Meier survival curves will be used to estimate survival outcomes. Cox proportional hazards regression analysis may be used to assess the association between survival and covariates of interest. The Fisher's exact test or logistic regression analysis will be used for any binary outcomes. T-tests or Wilcoxon rank sum tests will be used to compare continuous variables. Longitudinal models may be explored to study change over time.

Each subject's course will consist of three periods:

- A Pre-Treatment Period in which subjects are consented and undergo screening assessments to be qualified for the study (Section 5.1);
- A Treatment Period in which subjects receive study treatment and undergo study assessments (Section 5.2);

• A Post-Treatment Period in which subjects no longer receive study treatment but undergo follow-up study assessments and contacts (Section 5.3).

2.3 Treatment Assignment

It is the responsibility of the investigator to assign a subject number before treating each subject with cabozantinib.

2.4 Study Sites

This study will be conducted at one site - The University of Texas MD Anderson Cancer Center.

2.5 Withdrawals

Subjects may discontinue study treatment or withdraw their consent to participate in the study at any time without prejudice. The investigator may withdraw a subject from study treatment or from the study if, in his or her clinical judgment, it is in the best interest of the subject or if the subject cannot comply with the protocol.

In addition, any of the following conditions require discontinuation of the subject from study treatment:

- An AE or intercurrent illness that in the opinion of the investigator warrants the subject's withdrawal from study treatment;
- Specific conditions described in the Management of Adverse Events Sections 3.3.1 and 3.3.1.3;
- Necessity for treatment with other anticancer treatment prohibited by protocol;
- Sexually active subjects who refuse to use medically accepted barrier methods of contraception (eg, male condom, female condom) during the course of the study and for 4 months after discontinuation of study treatment;
- Women who become pregnant or are breastfeeding;
- If the subject does not recover from his or her toxicities to tolerable Grade ≤ 2 within 6 weeks, the subject will have study treatment discontinued unless there is unequivocal evidence that the subject is benefitting. In this situation, a subject may be able to restart therapy with a dose reduction upon resolution of the toxicity;

- Request by regulatory agencies for termination of treatment of an individual subject or all subjects under the protocol;
- Significant noncompliance with the protocol schedule in the opinion of the investigator;
- The minimum dose of study treatment will be 20 mg once daily (qd). Subjects who cannot tolerate 20 mg qd will have study treatment discontinued;
- Progressive disease (PD) as determined by the investigator unless the patient is deriving clinical benefit as judged by the investigator (case-by-case decision with approval of the Medical Monitor).

3 TREATMENTS

3.1 Composition, Formulation, and Storage

At study sites, all study medication will be stored as described in the pharmacy manual and inventoried in accordance with applicable state and federal regulations.

3.1.1 Investigational Treatment

Chemical Name: N-{4-[(6,7-dimethoxyquinolin-4-yl)oxy]phenyl}-

N'-(4-fluorophenyl)cyclopropane-1,1-dicarboxamide, (2S)-

hydroxybutanedioate

3.1.2 Cabozantinib Tablets

Exelixis internal number: XL184

Cabozantinib tablets are supplied as film coated tablets containing cabozantinib malate equivalent to 20 mg and 60 mg of cabozantinib and contain microcrystalline cellulose, lactose anhydrous, hydoxypropyl cellulose, croscarmellose sodium, colloidal silicon dioxide, magnesium stearate and Opadry® yellow. All tablet strengths are prepared from a common blend and are distinguished by shape. The 20 mg tablets are round and the 60 mg tablets are oval. The components of the tablets are listed in Table 3-1.

Table 3-1: Cabozantinib Tablet Components and Composition

Ingredient	Function	% w/w
Cabozantinib malate (25% drug load as cabozantinib)	Active Ingredient	31.7
Microcrystalline Cellulose (Avicel PH-102)	Filler	38.9
Lactose Anhydrous (60M)	Filler	19.4
Hydroxypropyl Cellulose (EXF)	Binder	3.0
Croscarmellose Sodium (Ac-Di-Sol)	Disenegrant	6.0
Colloidal Silicon Dioxide,	Glidant	0.3
Magnesium Stearate	Lubricant	0.75
Opadry Yellow Film Coating which includes: - HPMC 2910/Hypromellose 6 cp - Titanium dioxide Film Coating 4.00 - Triacetin - Iron Oxide Yellow		4.00

3.2 Dose, Schedule and Route

Subjects will receive cabozantinib orally at a starting dose of 60 mg once daily.

Cabozantinib must be taken on an empty stomach. Subjects must be instructed not to eat for at least 2 hours before and at least 1 hour after taking cabozantinib. Subjects should be instructed to take their cabozantinib dose at approximately the same time every day. If a subject misses a dose, the dose may be taken later only if it is within 12 hours of when the missed dose should have been taken. The missed dose should not be made up if it is within 12 hours of the next scheduled dose.

Cabozantinib tablets should be swallowed whole with at least 8 ounces of water. The tablets should not be crushed. Grapefruit, grapefruit juice, Seville oranges and their products should be avoided by subjects taking cabozantinib.

In all subjects, dose reductions and delays to manage toxicity are allowed under the guidelines in Section 3.3 below.

3.3 Cabozantinib Dose Modifications, Interruptions, and Discontinuation

Subjects will be monitored for AEs from the time of signing informed consent through 30 days after the date of the decision to permanently discontinue cabozantinib treatment. Subjects will be instructed to notify their physician immediately at the onset of any AE. Causality assessment of AEs should include at minimum confounding factors such as

disease and concomitant medications. AE severity will be graded by the investigator in accordance with CTCAE v.4.0.

The following should be taken into consideration in decisions regarding dose modifications (reductions or interruption):

- As a general approach all AEs should be managed with supportive care at the earliest signs of toxicity considered related to the study treatment. Should this be ineffective, dose interruptions and/or reductions should be considered to prevent worsening of toxicity.
- Dose modification criteria for cabozantinib are detailed in Section 3.3. Dose interruptions and/or reductions should be implemented for unacceptable toxicity. Doses may be modified at any time while on study.
- The assigned dose for cabozantinib is 60 mg/day. 20 mg dose reduction levels of cabozantinib are permitted (see Table 3-2).
- Dose reductions or interruptions may also occur in the setting of lower grade toxicity than defined in Sections 3.3.1 and 3.3.1.3, if the investigator feels it is in the interest of a subject's safety and will optimize drug tolerability.
- Interruption of cabozantinib treatment for AEs may occur at any time per investigator discretion. If treatment is interrupted due to AEs for more than 6 weeks, cabozantinib should be discontinued unless there is unequivocal evidence that the subject is benefitting. In this situation, a subject may be able to restart therapy with a dose reduction upon resolution of the toxicity.
- Dose interruptions for reason(s) other than AEs (eg, surgical procedures) can be longer than 6 weeks per the discretion of the investigator.

Guidelines for the management of specific AEs are provided in Section 3.3.1.3.

Table 3-2: Dose Reductions of Cabozantinib

Assigned dose	First Dose Level Reduction	Second Dose Level Reduction
60-mg cabozantinib oral qd	40-mg cabozantinib oral qd	20-mg cabozantinib oral qd

qd= once daily

Cabozantinib should be discontinued if a qd dose of 20-mg cabozantinib (minimum dose) is not tolerated

3.3.1 Management of Adverse Events

Guidelines for the management of AEs (ie, dose interruptions and dose reductions) are presented in the next sections (Sections 3.3.1 and 3.3.1.3). Each dose reduction of cabozantinib should be to one dose level lower that the current dose. Dose reductions of more than one dose level are acceptable if agreed to by the Investigator. All AEs should also be managed with supportive care at the earliest signs of toxicity considered related to the study treatment.

If study treatment of cabozantinib is restarted after being withheld or interrupted, the subject should be instructed not to make up the missed doses of cabozantinib.

The reason for treatment delay and reduced dose must be recorded on the case report form (CRF).

Dosing may need to be interrupted for AEs considered not related to cabozantinib if this is clinically indicated or if causality is initially uncertain. Study treatment may be resumed at the same dose (or a lower dose per investigator judgment) if the AE is determined not to be related to cabozantinib once the investigator determines that retreatment is clinically appropriate and the subject meets the protocol re-treatment criteria.

3.3.1.1 Cabozantinib Dose Reinstitution and Reescalation

If the subject recovers from his or her AE and the AE was unrelated to study treatment, then study treatment may be restarted with no change in dose.

Subjects receiving a daily dose of 20 mg may be restarted at the same dose if deemed safe at the discretion of the investigator. Subjects unable to tolerate a daily dose of 20 mg should discontinue study treatment.

Re-escalation to the previous dose, (but not higher than 60 mg/day) may be allowed at the discretion of the investigator but no sooner than 2 weeks beyond resolution of AEs that led to the dose reduction. Dose re-escalation is not allowed for a drug-related dose reduction triggered by myelosuppression or by Grade 4 AEs affecting major organs (eg, central nervous system, cardiac, hepatic, renal).

3.3.1.2 General Guidelines for Non-Hematologic and Hematologic Adverse Events

Table 3-3: General Approach to the Management of Cabozantinib-Related Non-Hematologic Adverse Events

CTCAE v4.0	Guidelines/Intervention
Grade 1:	Add supportive care as indicated. Continue cabozantinib at the current dose level if the AE is manageable and tolerable.
Grade 2 AEs which are tolerable and are easily managed	Continue cabozantinib treatment at the current dose level with supportive care.
Grade 2 AEs which are intolerable and cannot be adequately managed	 Interrupt cabozantinib treatment or dose reduction. Add supportive care as indicated. If cabozantinib dosing is interrupted, then upon resolution of the AE to baseline or Grade ≤ 1, cabozantinib may be resumed at either the same dose or with a dose reduction at the discretion of the investigator unless this is a recurring event at which time the dose should be reduced
Grade 3 AEs considered related to cabozantinib which occurred without optimal prophylaxis or which is easily managed by medical intervention or resolved quickly	 Interrupt cabozantinib treatment and add supportive care as indicated: For AEs that are easily managed (eg, correction of electrolytes) with resolution to baseline or Grade ≤ 1 within 24 hours, cabozantinib may be resumed at either the same dose or with a dose reduction at the discretion of the investigator unless this is a recurring event at which time the dose should be reduced For AEs that require supportive care, the dose should be held while supportive care is initiated and optimized. Then upon resolution of the AE to baseline or Grade ≤ 1, cabozantinib may be resumed at either the same dose or with a dose reduction at the discretion of the investigator unless this is a recurring event at which time the dose should be reduced
Grade 3 AEs considered related to study treatment that occurred despite optimal prophylaxis or is not easily managed by medical intervention	Interrupt cabozantinib treatment until recovery to ≤ Grade 1 or baseline, and resume treatment with a dose reduction.
Grade 4 AEs (except easily corrected laboratory abnormalities)	Permanently discontinue study treatment unless determined that the subject is unequivocally deriving clinical benefit. In this case, upon recovery to Grade ≤ 1 or baseline, the subject may be re-treated at a reduced dose that is to be determined by the investigator and MD Anderson Cancer Center/IND Office, but only with MD Anderson Cancer Center/IND Office approval.

Dose reductions or delays may occur in the setting of lower grade toxicity than defined above if the investigator believes that it is in the interest of the subject's safety.

Table 3-4: General Approach to the Management of Cabozantinib-Related Hematologic Adverse Events

CTCAE v4.0	Intervention
Neutropenia	
 Grade 3 neutropenia with infection requiring IV antibiotic, antifungal, or antiviral intervention Grade 3 neutropenia ≥ 7 days Grade 4 neutropenia 	Interrupt cabozantinib treatment until resolution to Grade ≤ 1 , and resume cabozantinib treatment at a reduced dose.
Thrombocytopenia	
Grade 3 thrombocytopenia with clinically significant bleeding or Grade 4 thrombocytopenia	Interrupt cabozantinib treatment until platelet count is ≥ 100,000/mm ³ , and resume cabozantinib treatment at a reduced dose.
Febrile Neutropenia	
Grade 3 febrile neutropenia	Interrupt cabozantinib treatment until recovery of ANC to Grade ≤ 1 and temperature to $\leq 38.0^{\circ}$ C and resume cabozantinib treatment at a reduced dose.
Grade 4 febrile neutropenia	Permanently discontinue study treatment unless determined that the subject is unequivocally deriving clinical benefit. In this case, upon recovery to Grade ≤ 1 or baseline, the subject may be re-treated at a reduced dose that is to be determined by the investigator and MD Anderson Cancer Center/IND Office but only with MD Anderson Cancer Center/IND Office approval.
Other Grade 4 Hematologic Toxicitie	es
Grade 4 hematologic toxicities other than anemia	Permanently discontinue study treatment unless determined that the subject is clearly deriving clinical benefit. In this case, upon recovery to Grade ≤ 1 or baseline, the subject may be re-treated at a reduced dose that is to be determined by the investigator and MD Anderson Cancer Center/IND Office, and only with approval by the MD Anderson Cancer Center/IND Office.
Grade 4 anemia	Permanent discontinuation for Grade 4 anemia is not mandated. Dose reductions or dose delays for anemia should be applied as clinically indicated. Supportive care such as red blood cell transfusions should be managed in accordance with institutional guidelines.

CTCAE v4.0 Intervention

ANC, absolute neutrophil count; LLN, lower limit of normal

Neutropenia: Grade 1 (ANC < LLN - 1.5×10^9 /L); Grade 2 (ANC < 1.5×10^9 /L - 1×10^9 /L); Grade 3 (ANC < 1×10^9 /L - 0.5×10^9 /L); Grade 4 (ANC < 0.5×10^9 /L).

Febrile Neutropenia: Grade 3 (present); Grade 4 (Life-threatening consequences; urgent intervention indicated).

Thrombocytopenia: Grade 1 (Platelet count <LLN - 75 x 10 9 /L); Grade 2 (Platelet count <75.0 - 50.0 x 10 9 /L); Grade 3 (Platelet count < 50 - 25 \times 10 9 /L); Grade 4 (Platelet count < 25 \times 10 9 /L).

.

3.3.1.3 Cabozantinib Warnings, Precautions, and Guidelines for Management of Specific Adverse Events

The side effect profile of cabozantinib includes GI symptoms (such as nausea, vomiting, and diarrhea, mucositis/stomatitis), fatigue/asthenia, anorexia, weight loss, skin disorders including palmar-plantar erythrodysesthesia (PPE) syndrome, elevated liver function tests (including alanine aminotransferase [ALT] and aspartate aminotransferase [AST]), osteonecrosis, increased pancreatic enzymes with rare cases of overt pancreatitis, thyroid function disorders, as well as side effects associated with inhibition of vascular endothelial growth factor (VEGF) signaling. The latter of these include arterial and venous thrombotic events such as deep vein thrombosis (DVT), pulmonary embolism (PE), transient ischemic attack, and myocardial infarction, hypertension, hemorrhagic events, proteinuria, wound complications, and rare cases of GI perforation, fistulae formation and rectal/perirectal abscess, and reversible posterior leukoencephalopathy (RPLS). Please refer to the Investigator's Brochure for additional details.

As with all investigational products, unknown AEs may occur. Subjects should be monitored closely for all AEs. As with other agents in development, additional AEs are unknown. As of 22 October 2013, in studies with cabozantinib angioedema has been reported to occur in ~0.1% of subjects treated.

The predicted effective plasma half-life of cabozantinib is 55 hours. Thus, when initiating therapy with cabozantinib, it will take most subjects 2 to 3 weeks to reach steady state. If AEs attributable to cabozantinib occur within the initial 3-week period of dosing, early intervention with dose modifications may be justified for AEs that, if worsened, could potentially be dangerous or debilitating, because without a dose adjustment, systemic exposure of cabozantinib might be expected to increase after the onset of the AE.

Management of diarrhea, nausea and vomiting, stomatitis and mucositis, hepatobiliary disorders (elevated ALT and AST), fatigue, anorexia and weight loss, skin disorders

(PPE and rash), wound healing, hypertension, thromboembolic events, proteinuria, QTc prolongation, hypophosphatemia, thyroid function disorders are presented in this section because these have been observed in previous studies with cabozantinib or represent common class effect toxicity. In addition, guidelines to minimize the risk for potential serious adverse events (SAEs) such as hemorrhagic events, GI and non-GI perforation and fistula formation, wound healing hemorrhagic events, and ONJ are provided in this section.

Please refer to the Investigator's Brochure for additional practice guidelines and management recommendations for side effects potentially related to cabozantinib treatment (such as asymptomatic elevations of amylase and lipase, pancreatitis, rectal and perirectal abscess, cardiac disorders, endocrine disorders, eye disorders, musculoskeletal and connective tissue disorders, nervous system disorders, respiratory, thoracic and mediastinal disorders); available information on potential risk of congenital, familial and genetic disorders; and guidelines on management of overdose of cabozantinib study treatment.

Below are guidelines for the treatment and/or prevention of certain treatment-emergent AEs of interest that have been associated with, or have a theoretical possibility of occurring with, cabozantinib treatment.

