3.3.1.9 Thromboembolic Events

Thromboembolic complications are frequent in cancer patients due to procoagulant changes induced by the malignancy or anticancer therapy including inhibitors of VEGF pathways. Deep vein thrombosis and PE have been observed in clinical studies with

cabozantinib; including fatal events (please refer to the Investigator's Brochure). Subjects who develop a PE or DVT should have cabozantinib treatment held until therapeutic anticoagulation with heparins (eg, low molecular weight heparin [LMWH]) is established. (Note: Therapeutic anticoagulation with oral anticoagulants, eg, warfarin, or oral platelet inhibitors such as clopidogrel is not allowed in this study). Cabozantinib treatment may be resumed in subjects who are stable and have uncomplicated PE or DVT and are deriving clinical benefit from cabozantinib treatment. During anticoagulation treatment, subjects need to be monitored on an ongoing basis for bleeding risk and signs of bleeding which may require additional or more frequent laboratory tests in accordance to institutional guidelines. If there are any signs of clinically significant bleedings, cabozantinib treatment should be permanently discontinued.

Arterial thrombotic events (eg, transient ischemic attack, myocardial infarction) have been observed in studies with cabozantinib. Subjects should be evaluated for preexisting risk factors for arterial thrombotic events such as diabetes mellitus, hyperlipidemia, hypertension, coronary artery disease, history of tobacco use, and cardiac or thromboembolic events that occurred before initiation of study treatment. Cabozantinib treatment should be discontinued in subjects who develop an acute myocardial infarction or any other clinically relevant arterial thromboembolic complication.

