3.3.1.14 Hemorrhagic Events

Hemorrhagic events have been reported with approved drugs that inhibit VEGF pathways as well as with cabozantinib. In order to mitigate risk of severe hemorrhage, subjects should be evaluated for potential bleeding risk factors before initiating cabozantinib treatment and monitored for bleeding events with serial complete blood counts and physical examination while on study. Risk factors for hemorrhagic events may include (but may not be limited to) the following:

- Tumor of the lung with cavitary lesions or tumor lesions which invades, encases, or abuts major blood vessels. The anatomic location and characteristics of tumor as well as the medical history must be carefully reviewed in the selection of subjects for treatment with cabozantinib;
- Recent or concurrent radiation to the thoracic cavity;
- Active peptic ulcer disease, ulcerative colitis, and other inflammatory GI diseases;
- Underlying medical conditions which affect normal hemostasis (eg, deficiencies in clotting factors and/or platelet function, or thrombocytopenia);
- Concomitant medication with anticoagulants or other drugs which affect normal hemostasis;
- History of clinically significant hemoptysis.

Discontinue cabozantinib treatment in subjects who have been diagnosed with a severe bleeding complication.

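### For Grade 3 thrombocytopenia with bleeding, Table 3-4 says hold and restart, but Sections 3.3.1.14 (severe bleeding) and 3.3.1.9 (bleeding on anticoagulation for PE/DVT) say stop

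*Combined protocol and SAP*

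**What the plan says.** Three places in the protocol set the action on study drug when a patient bleeds.

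- **Section 3.3.1.2, Table 3-4**, titled "General Approach to the Management of Cabozantinib-Related Hematologic Adverse Events". The thrombocytopenia row is triggered by "Grade 3 thrombocytopenia with clinically significant bleeding or Grade 4 thrombocytopenia". The action begins "Interrupt cabozantinib treatment until platelet count is" at least 100,000/mm³, followed by a restart at a lower dose. The point here concerns the part of the trigger that names bleeding.
- **Section 3.3.1.14, Hemorrhagic Events**: "Discontinue cabozantinib treatment in subjects who have been diagnosed with a severe bleeding complication". It gives no route back to treatment and makes no exception for bleeding with a low platelet count. Its list of bleeding risk factors includes "Underlying medical conditions which affect normal hemostasis (eg, deficiencies in clotting factors and/or platelet function, or thrombocytopenia", so patients with low platelets are within its scope.
- **Section 3.3.1.9, Thromboembolic Events**: "If there are any signs of clinically significant bleedings, cabozantinib treatment should be permanently discontinued". This sentence closes the paragraph on PE and DVT. The sentence before it begins "During anticoagulation treatment, subjects need to be monitored on an ongoing basis for bleeding risk and signs of bleeding".

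Section 2.5 (Withdrawals) lists what requires discontinuation of study treatment, and includes specific conditions described in Sections 3.3.1 and 3.3.1.3. None of these places defines *severe* or *clinically significant* bleeding, and none says which instruction prevails when two apply.

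**The concern.** A patient with Grade 3 thrombocytopenia who bleeds can meet the Table 3-4 row and one of the stop rules at once. A clinician who follows the table restarts the drug after platelet recovery; one who follows the event-specific section does not. Safety is at stake: following the table as written can re-expose a patient whom another section takes off treatment. Section 1.2.3.2.3 lists fatal hemorrhages among deaths not attributed to progression, and Section 7 states that there is no formal monitoring rule for toxicity.

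Data are at stake too. Table 5-1 schedules no tumor assessment in the post-treatment column, so whether a patient restarts or stops also decides whether scheduled imaging continues. That bears mainly on progression-free survival at 1 year.

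**Working it through.** The plan gives no figure to reproduce; the check compares texts. The cases below all assume Grade 3 thrombocytopenia. They take severe bleeding to be clinically significant as well, and read the Section 3.3.1.9 sentence within its paragraph, as covering patients anticoagulated for PE/DVT.

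| Bleeding | Anticoagulated for PE/DVT | Table 3-4 | 3.3.1.14 | 3.3.1.9 | Conflict |
|---|---|---|---|---|---|
| Clinically significant, not severe | No | Hold, then restart lower | Not triggered | Not triggered | None |
| Severe | No | Hold, then restart lower | Discontinue | Not triggered | Yes |
| Clinically significant, not severe | Yes | Hold, then restart lower | Not triggered | Permanently discontinue | Yes |
| Severe | Yes | Hold, then restart lower | Discontinue | Permanently discontinue | Yes, with both stop rules |

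There are thus two sources of conflict: severity of the bleed (against 3.3.1.14) and anticoagulation for PE/DVT (against 3.3.1.9). Because the two bleeding terms are undefined, the line between the first two rows of the table depends on individual judgment.

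**Does Section 2.5 settle it?** Its reference to Section 3.3.1 supports the stop rules. But Table 3-4 (in 3.3.1.2), 3.3.1.9 and 3.3.1.14 are all numbered under 3.3.1, so the reference does not rank one above another, and it does not mention the instruction to restart.

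**Can the anticoagulated case arise?** Therapeutic anticoagulation is excluded at entry (Section 4.2, criterion 9). However, Section 3.4.3 allows therapeutic low molecular weight heparin after the first dose, and Section 3.3.1.9 lets cabozantinib resume in stable patients with uncomplicated PE or DVT who are benefiting.

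**How often?** The documents give no rate for thrombocytopenia with bleeding. Two rough guides come from the pooled single-agent data in Section 1.2.3.2.1, which came from other tumors and include other doses:

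- PE of Grade 3 or above occurred in 5.9%: 22 × 0.059 = 1.3 patients. This gauges how many might be anticoagulated, not how many would also have low platelets and bleed.
- Thrombocytopenia is absent from the Grade 3-and-above list, which has a 5% threshold. If that list is complete, the expected number is below 22 × 0.05 = 1.1, before bleeding is also required.

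One affected patient is 1/22 = 4.5% of the trial, or 1/14 = 7.1% of the main branch.

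**The case against.** The strongest reply is that the passages can be read together. Table 3-4 is headed as a general approach and deals with the platelet count; the bleed is a separate event with its own stop rule; and Section 2.5 gives force to those rules. Section 2.5 also lets the investigator stop treatment for any adverse event that in his or her opinion warrants it, and with a single site (Section 2.4) there is no divergence between sites.

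This is a sensible reading, but the text does not state it. The Table 3-4 row is not purely about platelets: clinically significant bleeding is part of its trigger, and it still directs a restart. Discretion to stop does not remove a written instruction to resume, and a single site can still have clinicians who consult different sections.

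Other parts of the reply stand. Eligibility requires platelets of at least 100,000/mm³ and excludes recent clinically significant GI bleeding. The section on deaths does not link the fatal hemorrhages to thrombocytopenia. Best overall response keeps any response or stable disease documented before a stop, so the effect on the primary endpoint is limited.

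Three stronger readings are tempting and should not be adopted:

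- *Every patient with Grade 3 thrombocytopenia and clinically significant bleeding faces three competing rules.* The first case in the comparison shows otherwise: Section 3.3.1.14 needs severe bleeding, and the Section 3.3.1.9 sentence sits in the anticoagulation paragraph.
- *The row "Grade 4 hematologic toxicities other than anemia" contradicts the hold-and-restart rows for Grade 4 neutropenia and thrombocytopenia.* That row stands under a sub-heading for other Grade 4 toxicities, and both conditions have their own entries above it.
- *The same bleed may or may not need IND Office approval.* None of the three bleeding instructions mentions such approval.

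**Conclusion.** The contradiction is real but confined to two situations in a patient with Grade 3 thrombocytopenia: severe bleeding (Table 3-4 against Section 3.3.1.14), and clinically significant bleeding during anticoagulation for PE/DVT (Table 3-4 against Section 3.3.1.9). Outside them the protocol gives one instruction. Section 2.5 leans toward the stop rules without resolving the conflict.

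The size is qualitative: an uncommon combination, perhaps no patient or one among 22, with a safety consequence for that patient and little effect on the primary estimate. This rests on reading the Section 3.3.1.9 sentence within its paragraph, on severe bleeding also being clinically significant, and on the pooled adverse-event lists being a fair guide. It merits correction, but it does not threaten the trial's conclusions. The documents do not establish which action is clinically right, and no view on that is offered here.

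**What to change.** Reconcile the thrombocytopenia row of Table 3-4 with Sections 3.3.1.9, 3.3.1.14 and 2.5:

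1. Add a cross-reference from the row to the two bleeding passages, and state which instruction governs when more than one applies.
2. State whether the closing bleeding sentence of the PE/DVT paragraph in Section 3.3.1.9 is limited to anticoagulated patients.
3. Define, or at least distinguish, *severe* and *clinically significant* bleeding.

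The investigators and the IND Office decide which action stands in each situation. The cost is protocol wording in one amendment; sample size, analysis and visit schedule are unchanged.
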